9.6 Concomitant Treatments

9.6.1 Prohibited Concomitant Medications and Treatments

				No Medication/Treatment	Medications/Treatments Available		
drug	V1 ~ V2	V2 ~ V3	V3 ~ V4 2 weeks ago	2 weeks ago ~ V4			
NSAIDs	allowed			Not allowed			
Steroid injections (epidural adrenal cortex including hormone infusions)	Not allowed	allowed		Not allowed			
Oral steroids	Not allowed	allowed		Not allowed			
Anticoagulants	Not allowed						
Antiplatelet Drugs	Not allowed						
Fibrinolytic Agents	Not allowed						
Investigational devices Other anti-adhesion agents	Not allowed						

* Among the prohibited drugs, anticoagulants, antiplatelet drugs, and fibrinolytics are allowed as exceptions after discussion between the sponsor and the researcher.

9.6.2 Permitted Concomitant Medications and Treatments

During the clinical trial, the following drugs are allowed:

- 1) Concomitant medications that the subject has been taking prior to participating in this clinical trial and that are considered not to affect the interpretation of the results of this clinical trial are allowed at the discretion of the investigator.
- 2) Drugs used for the purpose of temporary treatment of other diseases should be administered in combination with the doctor in charge.
- 3) Among the prohibited concomitant medications, anticoagulants, antiplatelet agents, and fibrinolytic agents used for purposes other than anticoagulation, antiplatelet, and fibrinolytic drugs are exceptionally allowed after discussion between the sponsor and the researcher.

When administering all concomitant drugs (including therapeutic drugs in the event of other diseases or adverse events), information about the drug (product name, purpose of administration, dosage, start date of administration, end date of administration, etc.) is recorded in detail in the CRF and medical record.

10. OBSERVATION ITEMS - CLINICAL EXAMINATION ITEMS AND OBSERVATION TEST METHODS

10.1 Observations

10.1.1 Primary Efficacy Evaluation

Mean MRI Scar score between the test and control groups assessed by an independent evaluator at 6 weeks after the application of the investigational device

10.1.2 Secondary Efficacy Evaluation

- 1) Mean score on the 100-mm Visual Analogue Scale (VAS) for back pain in the test and control groups as assessed by subjects at baseline and at 3 and 6 weeks
- 2) Mean score on the 100-mm Visual Analogue Scale (VAS) for leg pain in the test and control groups as assessed by subjects at baseline and at 3 and 6 weeks
- 3) Mean score on the Oswestry Disability Index (ODI) for the limitation of daily living in the test and control groups as assessed by subjects at baseline and at 3 and 6 weeks

10.1.3 Safety Evaluation

- 1) Adverse Events
- 2) Laboratory tests, vital signs, physical examination

10.2 Clinical trial timeline

Refer to '1.2 Clinical Trial Schedule Summary'.

10.3 Inspection items by visit

10.3.1 Visit 1(Screening Visit, -4W~)

At Visit 1, procedures will be carried out to ensure that the voluntarily consented trial participants are suitable as subjects.

- Written consent
- Screening number assignment
- Demographic Survey
- Medications/Treatments Review
- Medical history
- Body Instrumentation
- Physical
- Laboratory tests
- Pregnancy test (only for women of childbearing potential)
- Vital signs

- Evaluation of Inclusion/Exclusion Criteria

10.3.2 Visit 2(Surgery, OD)

If the clinical trial participation is finally suitable through Visit 2, they will be randomized at this visit and receive the investigational device.

- Medications/Treatment Review
- Physical
- Laboratory tests
- Vital signs
- Evaluation of Inclusion/Exclusion Criteria
- Randomization
- 100 mm-VAS Evaluation (Waist & Legs)
- ODI Evaluation
- surgery
- Investigational device Application
- Check for adverse events

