Clinical Trials way	Procedure	
If subjects who meet the inclusion/exclusion criteria and voluntarily sign the consent form for the clinical trial are enrolled in this clinical trial, they will be treated with an investigational device or a control device during surgery for herniated disc or lumbar spinal stenosis and before surgical site closure. In addition, the procedure will be performed by the same investigator at each clinical trial site to minimize the impact of the procedure method. At 3 and 6 weeks after the application of the investigational device, safety Evaluations will be conducted and 3 and 6 weeks, VAS Evaluation for back and leg pain and Oswestry Disability Index (ODI) Evaluation for functional disability will be performed. In addition, MRI imaging of the medical device application area will be performed at 6 weeks after the application of the investigational device. The MRI of the subjects will be randomly assigned a new assignment number for each photo regardless of the assignment group by an independent data manager, and then sent to the independent evaluator with the subject's information completely excluded. The independent evaluator will evaluate the MRI Scar score evaluation criteria presented in this clinical trial by applying the same to each photo.
  
Clinical trial model

Investigational devices		
Investigational device: Collabarrier® Control device: Guardix-sol

Areas of application and How to apply		
Before applying this investigational device, all cleaning solution will be aspirated and removed, and all hemostatic agents (e.g., pads, sponges) will be removed. After confirming complete hemostasis in the wound area, the plug on the front part of the syringe is removed, and a medical spreader or catheter is inserted. Then, apply the test device or control device completely to the lateral surface of the nerve root, dorsal side, and the outer surface of the dura mater. The device was applied in a layer filling the area from the dorsal aspect of the nerve root and dura mater to the dorsal surface of the posterior lamina within the range of lamina resection. The amount applied was determined at the investigator's discretion according to the patient's condition, surgical site, and extent, with a maximum of 5 mL.

Prohibited Concomitant Medications/Treatments		 
No medication/ treatment Medications/Treatments Available

	drug	V1 ~ V2	V2 ~ V3	V3 ~ V4 2 weeks ago	2 weeks ago ~ V4				

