9. CLINICAL TRIAL METHODS

9.1 Clinical trial design

If subjects who meet the inclusion/exclusion criteria and voluntarily sign the consent form for the clinical trial are enrolled in this clinical trial, they will be treated with an investigational device or a control device during surgery for herniated disc or lumbar spinal stenosis and before surgical site closure. In addition, the procedure will be performed by the same investigator at each clinical trial site to minimize the impact of the procedure method. At 3 and 6 weeks after the application of the investigational device, subjects will be confirmed for safety, and 3 At 6 weeks, VAS Evaluation for back and leg pain and Oswestry Disability Index (ODI) Evaluation for limitation of daily life will be performed. In addition, MRI imaging of the medical device application area will be performed at 6 weeks after the application of the investigational device. The MRI of the subjects will be randomly assigned a new assignment number for each photo regardless of the assignment group by an independent data manager, and then sent to the independent evaluator with the subject's information completely excluded. The independent evaluator will evaluate the MRI Scar score evaluation criteria presented in this clinical trial by applying the same to each photo.

Clinical trial model

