9.2 Randomization Method

The randomization table will be prepared by a statistician who is not directly related to this clinical trial using SAS® (Version 9.4 or higher, SAS institute, Cary, NC, USA) so that each group can be assigned in a 1:1 ratio by stratified block randomization method considering the site as a stratification factor. Subsequently, subjects who participate in the clinical trial and meet the Inclusion/exclusion criteria will be sequentially assigned to each application group according to the randomization number, and the randomization number will be used as the subject identification code during the clinical trial.

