9.5.2 Blinding

This clinical trial was designed with subject and independent evaluator blinding. Since the two medical devices used in this clinical trial do not have an application and removal procedure in the subject's perceived situation, it is expected that a blinding design will be allowed, so this method was adopted. Since the investigator will know the treatment group assigned in advance by the application of the investigational device, blinding of the investigator is not allowed. However, this clinical trial is a controlled clinical trial, and in order to prevent bias in the primary efficacy endpoint, three radiology specialists were assigned as independent evaluators to maintain blinding during the evaluation of the primary endpoint. Attachment 7. Independent Evaluation Manual'.

The unique assignment code will be managed in a sealed state by the sponsor and the principal investigator of the clinical trial site, and the subject and investigator shall remain blinded to each subject's treatment arm assignment after the end of the study until the data management process is completed and the assignment code is released. If it is deemed necessary to release the subject's assignment code due to the occurrence of an emergency such as a serious adverse event, or if it is determined that it is absolutely necessary for the rights and safety of the subject, the blinding may be lifted according to the unblinding procedure.

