10.4.7 Evaluation of Inclusion/Exclusion Criteria and Assignment of Randomization Numbers

Based on the observations and examination items at Visit 1 and Visit 2, the Inclusion/exclusion criteria for suitability to participate in this clinical trial will be confirmed. Only subjects who are finally confirmed at Visit 2 will be assigned a registration number according to '9.3 Subject Assignment'.

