12.3 Subject dropouts

- 1) If the following are found during surgery
 - A. If there must be other devices left at the surgical site that may interfere with the interpretation of the study results
 - B. If dural rupture and dural hole are found during surgery
 - C. Epidural fat placement
 - D. If you have a herniated disc and need surgery on more than one level
 - E. If you are applying a sealant or making other attempts to repair a fibrous annulus tear
 - F. If a tumor in the spine is found during surgery
 - G. Entering the dura mater during surgery
 - H. If spinal fusion is required
 - I. If the hemostatic agent must remain at the surgical site
, but if it is cleaned after stopping the bleeding, it will not be dropped out.
 - J. If antibiotic powder is injected into the surgical site
(antibiotic cleaning is only allowed before the application of the medical device, not after applicati

on.)

K. When the following products are applied to exposed nerve elements

- Amniotic tissue or amniotic fluid
- adhesive
- steroid
- Platelet-rich plasma fluid
- Gel Foam
- Allograft tissue
- Fibrin Adhesive
- Dural patch

- 2) The subject (or legal representative) voluntarily wishes to discontinue the trial.
- 3) Surgery that may affect safety and efficacy evaluation, or when using other drugs and procedures in conjunction with other drugs and procedures
- 4) If an adverse event occurs during follow-up observation that makes it difficult to continue the clinical trial
- 5) Subjects who are not able to continue to follow up on the treatment of this clinical trial due to loss of contact during this clinical trial
- 6) Inclusion/exclusion criteria non-conformity confirmed since enrollment in the trial
- 7) If the principal investigator deems it inappropriate as a subject (if he does not comply with the investigator's instructions, if it is judged that he or she can no longer participate in the clinical trial in terms of safety or ethics due to a change in the subject's condition, etc.);

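### Minor: nothing keeps the sealed allocation closed until the intraoperative dropout criteria are checked, and a subject randomised but dropped before application is in no analysis set

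*Combined protocol and SAP*

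**What the plan says.** **When allocation happens.** Under 10.3.2, subjects finally found suitable at Visit 2 are those for whom "they will be randomized at this visit and receive the investigational device". That list, like the schedule in 1.2, puts randomisation above surgery and device application.

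**What allocation depends on.** In 9.2, subjects who "meet the Inclusion/exclusion criteria will be sequentially assigned to each application group according to the randomization number". In 10.4.7, "Only subjects who are finally confirmed at Visit 2 will be assigned a registration number", and the confirmation meant there is that of the inclusion/exclusion criteria.

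**When the device is applied.** Section 1.1 places treatment "during surgery for herniated disc or lumbar spinal stenosis and before surgical site closure".

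**Intraoperative criteria.** Section 12.3 item 1 lists findings A to K made during surgery and treats each as a dropout. Some are objective, such as dural rupture or a tumour. Others follow from what the surgeon does: epidural fat placement, annulus repair, products put on exposed nerve elements, or item J, "If antibiotic powder is injected into the surgical site".

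**Who operates and what they know.** In 9.1, "the procedure will be performed by the same investigator at each clinical trial site". In 9.5.2, "Since the investigator will know the treatment group assigned in advance by the application of the investigational device", blinding of the investigator is ruled out. The same section then says "The unique assignment code will be managed in a sealed state by the sponsor and the principal investigator" of the site, and that subject and investigator both stay blinded until the code is released. It does not say when the code is opened for a given operation.

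**Analysis sets and dropouts.** In 13.1 the FA Set needs application and a primary result, the PP Set (the main population) lies inside the FA Set, and the Safety Set needs application. Section 12.4 item 1 keeps dropout reasons. Item 3 includes dropouts in the analyses unless there is a valid reason not to. Section 13.2 leaves missing values uncorrected.

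**The concern.** A to K act as a second eligibility screen, but nothing makes them a condition of allocation. If the code is opened before that screen, a surgeon who knows the arm takes part in deciding who leaves the trial. Blinded MRI reading cannot repair this, because a subject excluded before application may have no study MRI to read. The usual check against selective exclusion, an analysis of everyone randomised, is not planned: the FA Set also omits subjects who never received the device. In a non-inferiority trial, selective loss can act in either direction. Losing poor outcomes mainly from the test arm makes non-inferiority easier to declare, and losing them mainly from the control arm makes it harder.

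**Working it through.** **1. The plan's own figure.** Inputs from 7.4: margin 0.57, SD 0.774, true difference 0, one-sided alpha 0.025, two-sample t-test. Power from the non-central t is 0.787 with 29 per arm and 0.80086 with 30 per arm, as printed. 30/(1 − 0.10) = 33.3, rounded up to 34 per arm, 68 in total. The figures reproduce, so this point does not rest on a sample-size error.

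**2. Set membership under 13.1.**

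| Subject | FA | PP | Safety |
|---|---|---|---|
| Randomised, dropped before application | no | no | no |
| Dropped after application (e.g. J or K), 6-week MRI obtained | yes | no | yes, once safety data exist |
| Dropped after application, no 6-week MRI | no | no | yes, once safety data exist |

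Section 12.4 item 3 does not change the first row. It names no set and does not say whether an A to K finding is a valid reason for leaving a subject out.

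**3. Illustration of size (assumed, not from the documents).** Assume 34 randomised per arm and excluded subjects scoring 0.5 point above the rest of their arm. Let the all-randomised difference equal the margin, 0.57, so that declaring non-inferiority is an error.

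- Bias in favour of the test arm = ((test losses − control losses)/34) × 0.5.
- For 3 test and 0 control losses: (3/34) × 0.5 = 0.044, which is 0.044/0.57 = 7.7% of the margin.
- Error = probability that the upper 95% limit is below 0.57 when the expected difference is 0.57 − bias (non-central t, SD 0.774).

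| Losses, test/control | Bias | One-sided error (nominal 2.5%) |
|---|---|---|
| 3/0 | 0.044 | 4.1% |
| 2/0 | 0.029 | 3.5% |
| 2/1 | 0.015 | 3.0% |
| 3/3 | 0 | 2.5% |
| 0/3 | −0.044 | 1.4% |

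With 0/3, power at a true difference of 0 is 77%, against 83% for the same 34 and 31 subjects without selection.

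**4. A ceiling from the plan's own scale.** The score runs from 0 to 4 (10.4.10). With 34 per arm, one unknown score can move the all-randomised mean difference by at most 4/34 = 0.118, or 0.118/0.57 = 21% of the margin. That is a loose limit. A change of one planning SD in one score moves it by 0.774/34 = 0.023, or 4% of the margin.

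**The case against.** **The text may already allow late allocation.** Order in a visit list need not be order in time. Section 10.4.7 draws on observations from Visit 2, which is the surgery visit, and some exclusion criteria overlap A to K (the need for other spinal surgery, for instance, overlaps spinal fusion). The 9.5.2 sentence can also be read as saying that the investigator learns the arm only at application. All of this stands. A reader might infer that the protocol orders randomisation before surgery; it does not. What remains is that late opening is permitted but nowhere required.

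**The main remedy may be too late.** Section 1.1 reports 69 subjects enrolled against a target of 68. This stands, and it reduces the practical point largely to reporting.

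**Late opening is only a partial cure.** Antibiotic powder (J) or products on the nerve (K) can follow application, and late opening does nothing for those. This stands.

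**The numbers are assumptions.** The 0.5-point shift and the loss patterns have no source in the documents. The 3/0 pattern is severe: if the same findings arise in both arms, it means that control subjects who met a criterion were kept. This stands, so the table shows direction and order of size only.

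**Power.** A reader might infer a shortfall. If 5% intraoperative loss came on top of the planned 10%, 34 × 0.95 × 0.90 = 29.07 would leave 29 per arm and power 0.787. But the 10% is not broken down by cause and may already cover these losses, so the documents do not support that claim.

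**Conclusion.** The gap is real and minor. No section holds the allocation until A to K have been checked, and a subject randomised and dropped before application falls outside all three analysis sets. Exclusion that depends on the arm is therefore not ruled out. A reader might go further and infer that such exclusion occurred, or that the trial's error rate is about 4%. Neither is supported: the documents give no intraoperative loss rate, no link between loss and arm, and no link between loss and scar score. If loss does not depend on the arm, no bias is expected. The set-membership result rests on the wording of 13.1 alone. The error rates rest on the assumptions stated with them.

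**What to change.** 1. **If any recruitment remains:** state in 9.2, 10.3.2 and 1.2 that the sealed allocation is opened only after the surgeon has recorded that none of A to K applies so far, immediately before application. A subject who meets a criterion earlier is not randomised. Cost: a short checklist and both devices kept ready in theatre (the test device is stored at 2 to 8 °C). Events under J or K after application are not covered and still need item 2.

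2. **If enrolment is complete:** report all randomised subjects by arm, with the reason for exclusion and whether it came before or after application, from the reasons already kept under 12.4 item 1. If any randomised subject is missing from the FA Set, add a supportive bounding or tipping-point analysis showing which missing scores, within 0 to 4, would bring the upper 95% limit to 0.57. State it as an exception to the no-correction rule in 13.2. Bounds suit this better than imputation from treated subjects, because a never-treated subject has no defined score under the assigned device. Cost: one table, one supportive analysis and one sentence in 13.2.

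3. **In either case:** reconcile the two statements on investigator blinding in 9.5.2, and reconcile 12.4 item 3 with the set definitions in 13.1. Cost: wording only. None of the three items needs extra patients or visits.

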10.3.3 Visit 3(Follow up, 3W±1W)

At 3 weeks after the application of the investigational device, subjects will visit the hospital and perform the following tests.

- Medications/Treatments Review
- Physical
- Vital signs
- 100 mm-VAS Evaluation (Waist & Legs)
- ODI Evaluation
- Check for adverse events

10.3.4 Visit 4(End Of Study, 6W±2W)

At 6 weeks after the application of the investigational device, subjects will visit the hospital for MRI scans, and the following tests will also be performed.

- Medications/Treatments Review
- Physical
- Laboratory tests
- Vital signs
- MRI imaging
- 100 mm-VAS Evaluation (Waist & Legs)
- ODI Evaluation
- Check for adverse events

10.3.5 Un-scheduled Visit

This is a visit that is conducted when additional irregular visits are required according to the investigator's judgment to confirm adverse events other than regular visits, and the schedule of regular

visits should not be changed due to such visits. Medications/Treatments Review and adverse event checks are performed, and physical examinations, laboratory tests, vital signs, MRI scans, and questionnaire evaluations (100 mm-VAS and ODI evaluations) may be performed if necessary.

10.4 Inspection method for each item

10.4.1 Obtaining written informed consent and granting a screening number

When the subject visits the institution for the first time to participate in this study, the investigator will explain to the subject about this study, answer the questions asked by the subject, and ask to participate in the study. If the subject agrees to participate in the study, a study number will be given according to '9.3 Subject Assignment'.

10.4.2 Demographic, drug/treatment, medical history

Demographic information (date of birth, gender, childbearing status) will be investigated at Visit 1.

In the case of prior drugs/treatments, drugs administered or being administered before the application of the investigational device within 4 weeks from the time of V1 will be investigated. The drug name (brand name or name name), purpose of administration, daily dose, unit, route of administration, and the start and end dates of administration are recorded, and information on the treatment performed before the application of the investigational device is also collected. At this time, it is judged whether the drug and treatment are continued, and if continuous prescription is required after the application of the investigational device, it is collected as a combination drug/treatment. In addition, information on the drugs administered after the application of the investigational device and the treatment performed will be collected.

Medical history will be examined at Visit 1. In the case of medical history, the presence or absence of past and current medical history, including diseases experienced or ongoing within 12 months or clinically significant medical conditions within 12 months at the time of V1, the time of occurrence (date of occurrence), whether it continues, and the opinion of the investigator will be recorded.

